**Figure 4: POSAS – Patient Scale**

**Figure 5: Posas – Observer scale**

## POSAS Observer scale

The Patient and Observer Scar Assessment Scale v2.0 / EN

Date of examination:

Name of patient:

### Observer

[figure not shown]
[figure not shown]
## Locations

**Date of birth:**

### **Research / studies**

---

**Identification number:**

### Explanation

The observer scale of the POSAS consists of six items (vascularity, pigmentation, thickness, relief, pliability and surface area). All items are scored on a scale ranging from 1 ('like normal skin') to 10 ('worst scar imaginable'). The sum of the six items results in a total score of the POSAS observer scale. Categories boxes are added for each item. Furthermore, an overall opinion is scored on a scale ranging from 1 to 10. All parameters should preferably be compared to normal skin on a comparable anatomic location.

#### **Explanatory notes on the items:**

- **VASCULARITY** Presence of vessels in scar tissue assessed by the amount of redness, tested by the amount of blood return after blanching with a piece of Plexiglas
- **PIGMENTATION** Brownish coloration of the scar by pigment (melanin); apply Plexiglas to the skin with moderate pressure to eliminate the effect of vascularity
- **THICKNESS** Average distance between the subcutical-dermal border and the epidermal surface of the scar
- **RELIEF** The extent to which surface irregularities are present (preferably compared with adjacent normal skin)
- **PLIABILITY** Suppleness of the scar tested by wrinkling the scar between the thumb and index finger
- **SURFACE AREA** Surface area of the scar in relation to the original wound area

Sponsor: Smith & Nephew

Negative Pressure Wound Therapy-PICO: Cosmesis in Repeat Cesarean Section

Device: PICO-7 Negative Pressure Wound Pump

NCT # 05266053

Document Date: 04/25/24

[name], Assistant Professor

Department of Obstetrics & Gynecology

[name]

[name]

Statistical Analysis:

We plan to enroll approximately 100 women with a previous C-section, which will be randomized 1:1 to either the standard dressing or PICO 7 dressing. The primary outcome will be the patient component of the Patient and Observer Scar Assessment Scale (POSAS) assessed at 2 weeks, 4 weeks, and 6 weeks following C-section. The primary time point of interest will be at 6 weeks since we expect the most improvement will be seen at the later time point. If approximately 20% drop-out by 6 weeks, then with $N = 80$ (40 per group), we will have 80% power to detect a .7 SD difference in mean scar assessment at 6 weeks between the two-groups using a two-sample t-test with equal variance and type I error set at 0.05 which provides conservative power compared to our linear mixed model. Based on a small RCT pilot study for C-section scars which used this instrument (Ekin et al., 2018), the effect sizes for the Patient, Observer, and Total POSAS were $ES = 1.18, 1.03$, and 1.15 , respectively. Also, the pooled SD was 7.2 for the Patient version, thus assuming our population will have a similar SD in this measure; we will be able to detect approximately a 5-point change (0.7×7.2) in Patient POSAS. Thus, we should have adequate power to detect meaningful improvements in scar assessment.

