### **Statistical Considerations**

We planned to enroll approximately 100 women with a previous C-section. If approximately 20% drop-out by 6 weeks, then with  $N = 80$  (40 per group), we will have 80% power to detect a .7 SD difference in mean scar assessment at 6 weeks between the two-groups using a two-sample t-test with equal variance and type I error set at 0.05 which provides conservative power compared to our linear mixed model. Based on a small RCT pilot study for C-section scars which used this instrument (Ekin et al., 2018), the effect sizes for the Patient, Observer, and Total POSAS were  $ES = 1.18, 1.03$ , and  $1.15$ , respectively. Also, the pooled SD was 7.2 for the Patient version, thus assuming our population will have a similar SD in this measure; we will be able to detect approximately a 5-point change ( $0.7 \times 7.2$ ) in Patient POSAS. Thus, we should have adequate power to detect meaningful improvements in scar assessment.

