### **Statistical Analysis:**

Characteristics of the study population were summarized using descriptive statistics. 24 patients were recruited and enrolled in the study. Out of these 24, only 3 patients that responded to all three (2-, 4- and 6- week) POSAS surveys. 15 patients responded to the 6 week assessment survey, which was the primary outcome of this study. For this reason, statistical analysis that would provide a statistically significant value was unable to be performed.

[figure not shown]

Figure 3: Enrollment and follow up

Results:

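### The stated 80% power for 0.7 SD with 40 per group does not follow from a type I error of 0.05; on a two-sided test the power is 87%

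*SAP*

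**What the plan says.** The SAP's Statistical Analysis text and the protocol's Statistical Considerations carry the same sample-size statement. About 100 women are to be enrolled. Allowing for 20% drop-out by 6 weeks leaves 80, that is 40 per group. With that number, the SAP says, "we will have 80% power to detect a .7 SD difference in mean scar assessment at 6 weeks between the two-groups". The test behind the figure is a "two-sample t-test with equal variance and type I error set at 0.05 which provides conservative power compared to our linear mixed model"; the protocol likewise names a "two-sample t-test with equal variance and type I error set at 0.05". Neither document says whether the test is one-sided or two-sided, and neither mentions a multiplicity adjustment or any level other than 0.05.

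The standardised difference is then put on the scale of the patient score. The SAP reports from a pilot trial that "the pooled SD was 7.2 for the Patient version", and both documents multiply 0.7 by 7.2. The protocol concludes that "we will be able to detect approximately a 5-point change".

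**The concern.** The power sentence fixes the number per group, the standardised difference, the test and the type I error. Apart from sidedness, nothing is left open, so the power can be calculated and compared with the stated 80%. The two do not agree.

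This statement is the only justification for the sample size in either document. If it cannot be reproduced from its own inputs, a reader cannot tell which input is wrong. If the power figure is wrong, the plan merely understates itself. If the type I error is wrong, the significance level that was planned is not the one written down. The protocol also calls for further, larger studies, and this calculation is a natural starting point for planning one.

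**Working it through.** **Inputs (SAP, repeated in the protocol's Statistical Considerations)**

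- Evaluable women: 100 × 0.8 = 80, or n = 40 per group with 1:1 allocation. This step is correct.
- Standardised difference: d = 0.7.
- SD of the patient score: 7.2, so 0.7 × 7.2 = 5.04 points. This step is also correct.
- Test: two-sample t-test, equal variance. Type I error α = 0.05.
- Sidedness: not stated. Two-sided is assumed first, then one-sided.
- Stated result: 80% power.

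**Formula**

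Under the alternative the t statistic follows a noncentral t distribution with

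- degrees of freedom 2n − 2 = 78
- noncentrality d × √(n/2) = 0.7 × √20 = 3.13

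Power is the probability that this variable falls beyond the critical value (in either tail, for a two-sided test).

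**Power for 0.7 SD, and the difference detectable with 80% power, at 40 per group**

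| Reading of the type I error | Critical t (78 df) | Power for 0.7 SD | Difference at 80% power | In points (× 7.2) |
|---|---|---|---|---|
| Two-sided 0.05 | 1.991 | 87.1% | 0.634 SD | 4.57 |
| One-sided 0.05 | 1.665 | 92.8% | 0.561 SD | 4.04 |
| Two-sided 0.025 | 2.285 | 79.9% | 0.701 SD | 5.04 |

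The stated 80% is not reproduced under either reading of 0.05. A one-sided 0.025 test has essentially the same power as the two-sided 0.05 test (87.1%), so it does not help. A simulation of 200,000 trials gave 87.1% at two-sided 0.05 and 79.8% at two-sided 0.025.

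**Attempts to recover 80%**

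- Normal approximation instead of t, two-sided 0.05: 87.9%.
- The rounded 5 points, d = 5/7.2 = 0.694: 86.6%.
- Solving for the two-sided level that gives exactly 80% at d = 0.7 and n = 40: α = 0.0252.
- Drop-out deducted twice, n = 40 × 0.8 = 32 per group, two-sided 0.05: 78.7% by t, 80.0% by the normal approximation.
- Number needed for 80% at d = 0.7, two-sided 0.05: 34 per group (81.2%), since 33 gives 79.97%.

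So 80% appears only if an input differs from what is written: the level (0.025) or the number per group (about 32 to 34).

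**The case against.** The strongest defence is that 80% is a conventional floor and not an exact figure. At two-sided 0.05 with 40 per group, 0.6 SD gives 75.5% and 0.7 SD gives 87.1%, so 0.7 is the smallest one-decimal effect that reaches 80%. Read that way, the sentence is true. But neither document says that 80% is a minimum. Both go on to treat 0.7 SD, about 5 points, as the detectable difference, and 0.634 does not round to 0.7. The reading is possible but not documented.

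A second defence is the remark about conservative power. It compares the t-test with the linear mixed model. The 80% is attributed to the t-test itself, so the remark does not explain the gap.

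Third, the match at 0.025 is numerical only and is no evidence of what was done; drop-out deducted twice, or a detectable difference rounded up, could equally be the cause. This stands, and the sponsor should be asked which inputs were used without a cause being presumed.

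Fourth, the practical weight is low, and this also stands. At 0.05 the planned number was ample for 0.7 SD, and the cited pilot effect sizes (1.18, 1.03 and 1.15) are well above 0.7. Only 24 women were enrolled, and the protocol's Statistical Analysis section reports that "statistical analysis that would provide a statistically significant value was unable to be performed".

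**Conclusion.** The stated power is wrong for the stated inputs. Assuming a two-sided 0.05 test, it is 87% and not 80%, an understatement of 7 percentage points. The difference detectable with 80% power is 0.63 SD and not 0.70, or about 4.6 points against about 5.0. If the test was meant to be one-sided at 0.05, the understatement is larger (92.8%).

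The conclusion rests on 40 evaluable women per group, equal variances and the SD of 7.2, all as given in the documents; only sidedness is assumed, and the finding holds either way. The documents do not show which input is at fault. The claim of adequate power for 0.7 SD survives, and no result in the report is affected. The defect is that the sole sample-size justification cannot be reproduced.

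**What to change.** In both the SAP and the protocol's Statistical Considerations, state the sidedness and confirm the type I error and the number per group that were actually used. Then:

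- If two-sided 0.05 with 40 per group is right, restate along these lines: with 40 evaluable women per group, a two-sided 0.05 two-sample t-test has 87% power for 0.7 SD (5.0 points at SD 7.2) and 80% power for 0.63 SD (4.6 points).
- If the calculation used a two-sided level of 0.025, keep 80% power for 0.7 SD and correct the stated type I error.
- If another input was used, such as a smaller number per group, say so and give the power for the 40 per group that the plan specifies.

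The cost is one sentence in each document, with no extra patients, no reanalysis and no change to any result.
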